4.2 Secondary Endpoints

The secondary endpoints include the incidence of all high-grade (Grades 3 and higher) select adverse events, the median time to onset and median time to resolution (Grades 3-4) of select adverse events, the and overall survival (OS) of subjects.

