8.2 Duration, On-study Event calculations

The duration between two dates will be calculated as [later date] – [earlier date] + 1 day. Study Day 1 or first dose date is the date of first study medication. Study day associated with an assessment will be calculated as [assessment date] – [first dose date (or enrollment date for non-treated subjects)], if the assessment is before first dose/enrollment; [assessment date] – [first dose date (enrollment for non-treated subjects)] + 1, if the assessment is on or after first dose/enrollment.

Events will be considered as occurring within X days (e.g., deaths within 30 days, deaths and AEs within 90 days) of last dose of study medication if [event date] – [last dosing date] ≤ X.

The following factors will convert days to months or years: 1 month = 30.4375 days, 1 year = 365.25 days.

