In order to derive the time-to resolution, overlapping or contiguous select AEs within a specific category (defined in [Table 5](#)) will be collapsed into what will be termed “clustered” select AEs. For example, if a subject (without pre-treatment AE) experienced an AE from 1st to 5th January, another AE (with different PT but within same category) from 6th to 11th January and same AE from 10th to 12th January, these will be collapsed into one clustered select AE from 1st to 12th January. [Table 4](#) is summarizing key derivation steps for each type of clustered select AEs.

Time-to resolution of select AE (any grade) for a specific category is defined as the longest time from onset to complete resolution or improvement to the grade at baseline among all clustered select AEs in this category experienced by the subject. Events which worsened into grade 5 events (death) or have a resolution date equal to the date of death are considered unresolved. If a clustered select AE is considered as unresolved, the resolution date will be censored to the last known date alive. Improvement to the grade at baseline implies that all different AE events in the clustered

select adverse event should at least have improved to the corresponding (i.e with same preferred term) baseline grade. This measure is defined only for subjects who experienced at least one select AE in the specific category.

The time-to resolution of select AE (grade 3-5) for a specific category is defined similarly with an onset date corresponding to a grade 3-5 select AE.

Time-to resolution of drug-related select AE (any grade or grade 3-5) is defined similarly but restricted to drug-related select AE.

The time-to resolution of select AE (any grade or grade 3-5, drug-related or all) where immune modulating medication was initiated is defined similarly with the additional condition that the subject started an immune modulating medication during the longest select AE resolution period.

Time-to resolution for a specific subcategory is defined similarly but restricted to event of this subcategory.

Table 4: Derivation of Clustered Select AE

Type of clustered select AE	Derivation
Any grade	
 • Collapse any on-treatment select AE from the same category
Drug-related of any grade	
 • Collapse any on-treatment drug-related select AE from the same category

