Grade 3-5	
 • Collapse any on-treatment select AE from the same category. • Resolution will be based on the onset date of the earliest grade 3-5 records (if no grade 3-5 record, clustered select AE is excluded)
Drug-related of Grade 3-5	
 • Collapse any on-treatment drug-related select AE from the same category • Resolution will be based on the onset date of the earliest grade 3-5 record (if no Grade 3-5 record, clustered select AE is excluded)

The algorithm for collapsing select adverse event records is using the following conventions:

For each subject and specified category, the corresponding adverse event records will be collapsed when:

- 1) Multiple adverse event records have the same onset date.
- 2) The onset date of an event record is either the same day or 1 day later than the resolution date of a preceding event record (contiguous events).
- 3) The onset date of an event record is after the onset date and prior to or on the resolution date of a preceding event record (overlapping events).

Table 5: Select Adverse Events

Category	Subcategory	Preferred Term
ENDOCRINE ADVERSE EVENT	ADRENAL DISORDER	ADRENAL INSUFFICIENCY
		ADRENAL SUPPRESSION
		ADRENOCORTICAL INSUFFICIENCY ACUTE
		BLOOD CORTICOTROPHIN DECREASED
		BLOOD CORTICOTROPHIN INCREASED
		HYPOTHALAMIC PITUITARY ADRENAL AXIS SUPPRESSION
		SECONDARY ADRENOCORTICAL INSUFFICIENCY
	DIABETES	DIABETES MELLITUS
		DIABETIC KETOACIDOSIS
		FULMINANT TYPE 1 DIABETES MELLITUS
		LATENT AUTOIMMUNE DIABETES IN ADULTS
		TYPE 1 DIABETES MELLITUS
	PITUITARY DISORDER	HYPOPHYSITIS
		HYPOPITUITARISM
		LYMPHOCYTIC HYPOPHYSITIS
	THYROID DISORDER	ATROPHIC THYROIDITIS
		AUTOIMMUNE HYPOTHYROIDISM
		AUTOIMMUNE THYROIDITIS
		BASEDOW'S DISEASE
		BLOOD THYROID STIMULATING HORMONE DECREASED
		BLOOD THYROID STIMULATING HORMONE INCREASED
		HYPERTHYROIDISM
		HYPOTHYROIDISM

Table 5: Select Adverse Events

Category	Subcategory	Preferred Term
		PRIMARY HYPERTHYROIDISM
		PRIMARY HYPOTHYROIDISM
		THYROID FUNCTION TEST ABNORMAL
		THYROID HORMONES DECREASED
		THYROID HORMONES INCREASED
		THYROIDITIS
		THYROIDITIS ACUTE
		THYROXINE DECREASED
		THYROXINE FREE DECREASED
		THYROXINE FREE INCREASED
		THYROXINE INCREASED
		TRI-IODOTHYRONINE UPTAKE INCREASED
GASTROINTESTINAL ADVERSE EVENT		AUTOIMMUNE COLITIS
		COLITIS
		COLITIS ULCERATIVE
		DIARRHOEA
		ENTERITIS
		ENTEROCOLITIS
		FREQUENT BOWEL MOVEMENTS
		GASTROINTESTINAL PERFORATION

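### Time to resolution of select AEs: the longest-cluster rule can record a subject as resolved while another cluster in the same category is unresolved or fatal

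*SAP*

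**What the plan says.** SAP Appendix 1 derives time to resolution in three steps.

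- **Clustering.** Records in one category merge when they overlap or touch. The test for touching is: "The onset date of an event record is either the same day or 1 day later than the resolution date of a preceding event record". Records further apart remain separate clusters.
- **Status and end date.** "Events which worsened into grade 5 events (death) or have a resolution date equal to the date of death are considered unresolved". Then: "If a clustered select AE is considered as unresolved, the resolution date will be censored to the last known date alive".
- **One value per subject.** The subject's time is the "longest time from onset to complete resolution or improvement to the grade at baseline among all clustered select AEs in this category".

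The Grade 3-5, drug-related, immune-modulating-medication and subcategory versions are derived in the same way, so they inherit the rule. In the Grade 3-5 version, Table 4 drops a cluster that has no Grade 3-5 record.

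SAP 4.2 lists "median time to resolution (Grades 3-4) of select adverse events" among the secondary endpoints, as does protocol 8.3.2. The matching objective in SAP 3.2 is to characterise the outcome of high-grade select AEs.

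No sentence in either document says how a censored cluster time ranks against a completed one, or gives an unresolved cluster precedence. SAP 7.6.2.2 points to section 7.6.6 of the Core Safety SAP for this analysis, and SAP 8 allows further conventions in the Data Presentation Plan. Neither is among the documents reviewed.

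**The concern.** The quantity wanted is the longest time a subject needed to resolve an event in a category. If one cluster resolved and another did not, that maximum was not observed. It is known only to be at least as long as the resolved cluster, so the correct status is censored.

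Appendix 1 compares observed lengths instead. Death or last contact cuts the unresolved cluster short, so the resolved one can win and the subject counts as an observed resolution. The unresolved cluster then contributes nothing, not even censoring. The opposite error cannot occur, so the count of resolved subjects can only be too high.

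Two features of the plan make this more than a curiosity. Protocol 4.6.3 lets treatment resume after resolution, so a resolved cluster followed by another in the same category is a foreseeable course. SAP 7.6.3 also tabulates time to resolution by type of autoimmune disorder, where groups may be small and one misclassified subject would show.

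**Working it through.** **1. The SAP's own example.** The records run 1-5, 6-11 and 10-12 January. The second starts one day after the first ends (6 = 5 + 1) and the third starts before the second ends (10 < 11), so "these will be collapsed into one clustered select AE from 1st to 12th January". SAP 8.2 counts the later date minus the earlier date plus 1 day: 12 - 1 + 1 = 12 days. The example reproduces.

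**2. The rule applied to constructed subjects** (days are hypothetical; last known date alive is taken as the day of death in the fatal case).

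| Subject | Cluster A | Cluster B | Appendix 1 gives | Correct status |
|---|---|---|---|---|
| 1 | days 20-80, resolved: 80 - 20 + 1 = 61 | days 120-130, fatal: 130 - 120 + 1 = 11 | max(61, 11) = 61, resolved | at least 61, censored |
| 2 | days 20-30, resolved: 11 | from day 120, unresolved, alive day 400: 400 - 120 + 1 = 281 | 281, censored | 281, censored |

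Only subject 1 is wrong. Nothing depends on the 61 days: a resolved cluster of 12 days, as in the SAP's January example, would also outrank an 11-day fatal one.

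**3. Effect on a count.** Take 20 subjects with resolved clusters of 10, 20, ..., 200 days, where k of those with clusters longer than 10 days later have a separate 10-day fatal cluster. Appendix 1 reports 20 of 20 resolved for k = 2, 4, 6 and 8. The number with every cluster resolved is 20 - k = 18, 16, 14 and 12.

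**4. Illustrative size.** The documents give no recurrence or duration figures, so all inputs are assumptions: exponential cluster durations and gap, each with mean 60 days; exponential follow-up from first onset with mean F = 180 or 365 days; a share p = 10% or 40% of affected subjects prone to a second cluster.

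- Chance that follow-up ends before a cluster resolves: q = 60 / (60 + F), which is 0.250 or 0.141.
- Share of subjects with two clusters: p(1 - q)².
- Second cluster unresolved, given two: q.
- Resolved cluster longer than the observed part of the unresolved one: 1/2, because both observed lengths then have the same exponential distribution.
- Correct unresolved share: q + p(1 - q)²q.
- Understatement: p(1 - q)²q / 2. For F = 180 and p = 40%: 0.4 × 0.75² × 0.25 / 2 = 0.028.

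The Kaplan-Meier medians come from simulation under the same assumptions (400,000 affected subjects, mean of 20 runs). The last column but one censors at the longest observed cluster time.

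| F (days) | p | Unresolved, correct | Unresolved, Appendix 1 | Gap (points) | Median, Appendix 1 | Median, corrected | Shift (days) |
|---|---|---|---|---|---|---|---|
| 180 | 10% | 26.4% | 25.7% | 0.7 | 43.67 | 43.98 | 0.3 |
| 180 | 40% | 30.6% | 27.8% | 2.8 | 50.05 | 51.60 | 1.6 |
| 365 | 10% | 15.2% | 14.6% | 0.5 | 44.10 | 44.28 | 0.2 |
| 365 | 40% | 18.3% | 16.2% | 2.1 | 51.91 | 52.86 | 0.9 |

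The correction turns some events into censorings at the same times. Risk sets stay the same and events fall, so the estimated median cannot become shorter.

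**5. Where it concentrates.** For independent exponential times with medians R (resolved) and U (observed unresolved), the resolved cluster is longer with probability R / (R + U). With R = 28 days (an assumption), this is 28/35 = 80% for U = 7 days and 28/208 = 13% for U = 180 days. The problem lies in rapidly fatal events and events that start near last contact.

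**The case against.** **The named endpoint is a median, and it barely moves.** This stands: the shift is about 0.2 to 1.6 days on medians of 44 to 53 days. The resolved count moves more, but only by a few percentage points.

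**The protocol limits recurrence.** Protocol 4.6.4 calls for permanent discontinuation after a drug-related, non-skin Grade 3 event lasting more than 7 days, after most Grade 4 drug-related events, and after interruptions of more than 6 weeks, with stated exceptions. Table 4 of the SAP clusters only on-treatment events. A long drug-related Grade 3 episode followed months later by a second one would often fall outside the analysis. This stands too, and 40% recurrence is probably too high for drug-related Grade 3-4 events. Room remains for skin events, short Grade 3 episodes, unrelated events and the listed exceptions.

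**A reader might infer that fatal events vanish from the safety report.** The documents do not support that. Grade 3 or higher incidence, which includes Grade 5, is the primary endpoint for treatment-related select AEs and a secondary endpoint regardless of relationship. SAP 7.6.3 reports deaths and serious AEs separately.

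**The ranking by observed length is inferred.** It follows from assigning an end date to the unresolved cluster before taking the longest. The Core Safety SAP or the Data Presentation Plan may say otherwise. If an unresolved cluster is treated there as longest by default, the problem disappears.

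**Replacing the subject's value with the unresolved cluster would lose information.** For subject 1 it would swap a known 61 days for 11 censored days. In the 20-subject set it moved the median from 100 to between 80 and 100 days. This is a good argument against that remedy, but not against censoring at the longest observed time, which keeps the 61 days.

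**Conclusion.** The point holds as a limited defect in a derivation rule. As Appendix 1 reads, a subject with an unresolved or fatal cluster enters as resolved whenever a separate resolved cluster in the same category is longer than its observed time. That conclusion follows from the text and needs no numerical assumption.

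The size does need assumptions, and the documents supply none of them. In the illustrated range, the unresolved share is understated by about 0.5 to 3 percentage points and the median by about 0.2 to 1.6 days. Two conditions limit the reach: the subject must have at least two separate clusters in the category, and the Core Safety SAP must not already contain a ranking rule. The documents do not support a claim that the secondary endpoint is seriously distorted, nor any effect on the primary endpoint.

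**What to change.** In the time-to-resolution definition of SAP Appendix 1, state that:

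- if any cluster in the category is unresolved or fatal, the subject is counted as unresolved and censored at the longest observed cluster time in that category;
- the subject is counted as resolved, at the longest time, only if all clusters in the category resolved;
- the same rule applies to the Grade 3-5, drug-related, immune-modulating-medication and subcategory versions.

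Beside each median, report the number and percentage of subjects with any unresolved or fatal cluster. Kaplan-Meier treats death as ordinary censoring under either rule, so this count is what shows the fatal outcomes in this summary. If the Core Safety SAP already ranks unresolved clusters first, repeat or cite that rule in Appendix 1 and check that it agrees.

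The cost is one programming condition and one table row. The reported resolution figure becomes slightly less favourable. No extra data are needed.

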Stop the nivolumab infusion, begin an IV infusion of normal saline, and treat the patient with diphenhydramine 50 mg IV (or equivalent) and/or paracetamol 325 to 1000 mg (acetaminophen); remain at bedside and monitor patient until resolution of symptoms. Corticosteroid or bronchodilator therapy may also be administered as appropriate. If the infusion is interrupted, then restart the infusion at 50% of the original infusion rate when symptoms resolve; if no further complications ensue after 30 minutes, the rate may be increased to 100% of the original infusion rate. Monitor patient closely. If symptoms recur then no further nivolumab will be administered at that visit. Administer diphenhydramine 50 mg IV and remain at bedside and monitor the patient until resolution of symptoms. The amount of study drug infused must be recorded on the electronic case report form (eCRF). The following prophylactic medications are recommended for future infusions: diphenhydramine 50 mg (or equivalent) and/or paracetamol 325 to 1000 mg (acetaminophen) should be administered at least 30 minutes before additional nivolumab

administration. If necessary, corticosteroids (recommended dose: up to 25 mg of IV hydrocortisone or equivalence) may be used.

Grade 3 or 4 symptoms (severe reaction, Grade 3 prolonged [ie not rapidly responsive to symptomatic medication and/or brief interruption or infusion]; recurrence of symptoms following initial improvement; hospitalization indicated for other clinical sequelae [eg, renal impairment, pulmonary infiltrates]). Grade 4: (life-threatening, pressor or ventilatory support indicated):

Immediately discontinue infusion of nivolumab. Begin an IV infusion of normal saline and treat the patient as follows: recommend bronchodilators, epinephrine 0.2 to 1 mg of 1:1,000 solution for subcutaneous administration or 0.1 to 0.25 mg of 1:10,000 solution injected slowly for IV administration, and/or diphenhydramine 50 mg IV with methylprednisolone 100 mg IV (or equivalent) as needed. Nivolumab will be permanently discontinued. Investigators should follow their institutional guidelines for the treatment of anaphylaxis. Remain at bedside and monitor patients until recovery from symptoms. In the case of late-occurring hypersensitivity symptoms (eg, appearance of a localized or generalized pruritus within 1 week after treatment), symptomatic treatment may be given (eg, oral antihistamine or corticosteroids).

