7.6.3 Other Safety Analysis

Other safety analysis will be conducted as below as specified in the Core Safety SAP, according to the general methods:

- Deaths
- Serious adverse events
- Adverse events leading to discontinuation of study therapy
- Adverse events leading to dose modification
- Adverse events
- Multiple adverse events
- Laboratory parameters
- Vital signs
- Pregnancy
- Adverse events by demographic subgroups

A summary by type of autoimmune disorder will be presented for the following adverse events tables.

- Any adverse events
- Drug-related adverse events
- Drug-related serious adverse events
- Drug-related adverse events leading to discontinuation
- Drug-related select adverse events
- Drug-related select adverse events leading to discontinuation
- Any adverse events that required immune modulating medications
- Time to resolution of drug-related select adverse events
- Time to resolution of drug-related select adverse events where immune modulating medications was initiated
- Time to onset of drug-related select adverse events

■ [REDACTED]

A subject listing of prior immune modulating medications (subjects with any prior immune modulating medication, subjects by medication class and generic term) will be presented. This would include immune modulating medications taken on or before first dose of study therapy.

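### SAP Appendix 1 checks for immune modulating medication only after picking each subject's longest cluster, so subjects whose treated cluster was shorter drop out of that time-to-resolution analysis

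*SAP*

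**What the plan says.** SAP Appendix 1 first merges overlapping or contiguous select AEs of one category into clusters. Time to resolution is then the "longest time from onset to complete resolution or improvement to the grade at baseline among all clustered select AEs in this category" that the subject had. On who enters: "This measure is defined only for subjects who experienced at least one select AE in the specific category". On unresolved events: "If a clustered select AE is considered as unresolved, the resolution date will be censored to the last known date alive".

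The IMM version, in its any-grade, Grade 3-5, drug-related and all-cause forms, is derived in the same way "with the additional condition that the subject started an immune modulating medication during the longest select AE resolution period". SAP 7.6.3 (Other Safety Analysis) lists the resulting table, by type of autoimmune disorder, as "Time to resolution of drug-related select adverse events where immune modulating medications was initiated".

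The other restricted versions work in a different order. In the text and Table 4 of Appendix 1, the drug-related version collapses only drug-related events, and the Grade 3-5 version discards any cluster without a Grade 3-5 record. In both, the longest is chosen from what remains.

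**The concern.** Read literally, the IMM version picks the longest cluster among treated and untreated alike, and only then asks whether IMM was started during it. A treated cluster therefore counts only if it outlasts every untreated cluster of that subject in the category. Duration is the outcome, so inclusion depends on the outcome.

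The table's label leads a reader to expect every subject with an IMM-treated event. What the rule delivers is the subset whose longest event was treated. The censoring rule can add to this: an untreated event that never resolves runs to the last date known alive, and so easily becomes the longest and displaces an earlier treated event that resolved.

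At stake is a description of how select AEs resolve once immunosuppression is started. That bears on the secondary objective of characterising the outcome of high-grade select AEs, although the table itself is not a named endpoint.

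**Working it through.** The plan states no figure for this analysis, so there is none to reproduce. Applying the collapsing rules to the SAP's own example (events on 1-5, 6-11 and 10-12 January) gives one cluster, as stated: "these will be collapsed into one clustered select AE from 1st to 12th January".

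**Step 1. The rule on simple cases (illustrative lengths, separate clusters, one category).**

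| Treated cluster | Untreated cluster | Longest | Value under Appendix 1 | Value if restricted first |
|---|---|---|---|---|
| 30 days | 10 days | treated | 30 | 30 |
| 10 days | 30 days | untreated | none, subject out | 10 |
| 20 days, Grade 3 rash | 60 days, low-grade pruritus | untreated | none in the any-grade version | 20 |

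In the last row the Grade 3-5 version still keeps the subject, because Table 4 removes the pruritus cluster. To lose a subject there, two separate Grade 3-5 clusters in one category are needed, the longer one untreated.

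**Step 2. Size under independence.** All inputs are assumptions. Each treated subject has one treated cluster with duration T ~ exponential, mean 1 (median ln 2 = 0.693). A share f also has one untreated cluster U ~ exponential, mean m. The subject is kept if there is no second cluster or if T > U.

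- P(T > U) = 1/(1 + m), so the share dropped is f × m/(1 + m).
- For m = 1, put u = 1 − e^(−t). The retained median solves (1 − f)u + (f/2)u² = ½(1 − f/2).
- At f = 0.30: 0.15u² + 0.70u − 0.425 = 0, so u = 0.544, t = 0.785, and 0.785/0.693 = 1.13.
- For m = 2 the equation is (1 − e^(−t)) − (2f/3)(1 − e^(−1.5t)) = ½(1 − 2f/3).

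| f | Dropped, m = 1 | Median ratio, m = 1 | Dropped, m = 2 | Median ratio, m = 2 |
|---|---|---|---|---|
| 0 | 0% | 1.00 | 0% | 1.00 |
| 0.15 | 7.5% | 1.06 | 10% | 1.05 |
| 0.30 | 15% | 1.13 | 20% | 1.11 |
| 0.50 | 25% | 1.26 | 33% | 1.23 |

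A second model agrees. It uses log-normal durations (assumed median 28 days, log-SD 1), a second cluster in 10% to 50% of subjects, and 30% to 70% of clusters treated. The rule then excludes 3% to 26% of subjects with any treated cluster. The median is 2% to 26% above that of each subject's longest treated cluster, for example 33.7 against 30.4 days (33.7/30.4 = 1.11).

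**Step 3. Does the sign hold?** Correlating durations within a subject, without changing who has a second cluster, leaves the rise at 11% to 12% (log-normal, f = 30%, subject log-SD up to 1). Now let subjects with long clusters also be more likely to have a second one. In the exponential model, a shared subject effect acts on log duration (SD s) and on the log-odds of a second cluster (slope s), around a 30% baseline:

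| s | Median ratio, m = 1 | Median ratio, m = 2 |
|---|---|---|
| 1.0 | 1.03 | 0.95 |
| 1.5 | about 0.9 | 0.81 |

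In the log-normal model the same kind of dependence gives differences from +5% to −34%. The sign turns because the excluded subjects then tend to have long clusters throughout, and even their shorter treated cluster can exceed the retained median.

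**The case against.** The strongest reply is that the effect is small and its direction unknown. Several parts of it stand.

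- **Direction.** A reader might infer that the median is certainly biased upward. Step 3 shows that it need not be, and the documents give no cluster counts or correlations to settle it. Each retained value is also correct as a subject's longest cluster; the defect is who is left out.
- **Severe treated events.** A reader might infer that a steroid-treated Grade 3 event vanishes altogether. It is lost only from the any-grade version when a longer untreated cluster exists, and is normally still counted in the Grade 3-5 version.
- **Clustering.** Events that overlap or abut within a category are merged even when the preferred terms differ, so many treated and untreated events will form one treated cluster and the subject stays in. Nothing in the documents shows which categories would be hit hardest.
- **Importance.** A reader might infer that a secondary endpoint is affected. Median time to resolution in Protocol 8.3.2 and SAP 4.2 carries no medication condition. Nor can this table be called the only account of resolution under IMM: part of SAP 7.6.3 is redacted, outputs are deferred to the Data Presentation Plan, and Core Safety SAP Section 7.6.6 is not among the documents.
- **Day 1 medication.** SAP 7.6.3 says of its prior-medication listing: "This would include immune modulating medications taken on or before first dose of study therapy". A reader might infer that a steroid given on the day of first dose is therefore barred from the IMM analysis. That text describes a listing and bars nothing, and SAP 8.1 defines baseline results, not medications.

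The reply does not remove the exclusion. It follows from the wording of Appendix 1, differs from the order used in the drug-related and Grade 3-5 versions, and is given no reason in the supplied text.

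**Conclusion.** The point holds in a limited form. The IMM condition is applied after the maximum, so treated subjects are excluded according to how long their treated cluster lasted relative to their untreated ones. With independent clusters of equal mean length, and a second untreated cluster in 15% to 50% of treated subjects, the median is about 6% to 26% too long. Those rates are assumed, and under plausible dependence the sign can reverse. The effect is zero with one cluster per subject and category. It is mainly an issue for the any-grade versions and is confined to a descriptive safety analysis. It merits correction because the output does not match its label and the change is cheap, not because any main conclusion of the trial depends on it.

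**What to change.** In SAP Appendix 1, reverse the order: restrict first to clustered select AEs during which an IMM was started, then take the longest of those per subject and category. Apply this to the any-grade, Grade 3-5, drug-related and all-cause versions. Report alongside it the number of subjects whom the current rule would have excluded, so that readers can see whether the choice mattered.

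The cost is a sentence in the SAP and one re-ordered programming step, with no new data. The downside is that the figure may differ slightly from other studies in the program that use the existing derivation; the count of excluded subjects would help to explain a difference.
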